Systemic lupus erythematosus (SLE) is a prototypic autoimmune disease whose heterogeneity has confounded scientists, clinicians, and patients for decades. Current therapeutic efforts are directed at the inflammation that causes organ damage, yet patients often remain disabled by fatigue, myalgia, mood disturbance, and cognitive dysfunction. These symptoms are persistent and often resistant to immunosuppression.

At Duke, we have developed a new conceptual model that characterizes SLE activity into two dimensions:

- Type 1: Classically considered SLE activity and recorded in physician-reported measures of SLE activity. Includes synovitis, rashes, serositis, nephritis, CNS lupus, and other objective signs.
- Type 2: Symptoms of fatigue, myalgia, mood disturbance, and cognitive dysfunction; typically not included in physician-reported measures of SLE, but are frequently reported by patients. Physicians

may ascribe these symptoms to depression or fibromyalgia, while patients identify them as SLE-related.

We hypothesize that Type 1 and 2 SLE activity varies in intensity over time, including some periods of minimal activity (neither Type 1 or 2) and mixed activity (both Type 1 and 2).

Patient-reported measures have had limited acceptance in the study of SLE, possibly due to the incongruence between Type 1 physician-reported activity and Type 2 patient-reported symptoms. According to over 1000 patients with SLE, a patient-defined-flare includes extreme fatigue (87% of the flares), aching joints (80%), muscle weakness or pain (74%), and forgetfulness (61%). Of these symptoms, only aching joints would be counted as active lupus by a rheumatologist; the remaining symptoms are likely Type 2 activity of SLE. While the authors of this study suggested that we need to re-educate our patients about lupus flares, we suggest we change how we think about SLE.

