In-depth interviews: Interviews will be audio-recorded and transcribed verbatim. Nvivo, a qualitative research software, will be used to facilitate analysis. First, we will each apply the same structural codes to group similar responses together. Thematic coding will follow, focusing on identifying the main themes and sub-themes for each conceptual group (Guest 2006). Intercoder reliability procedures will be conducted; discrepancies in coding will be discussed, resolved, and revised as necessary. Thematic code frequencies across transcripts will be examined to identify the most frequent and salient themes, and data

reduction techniques will be used to explore the nuances and to identify sub-themes. Descriptions of these themes and sub-themes, together with illustrative quotes, will be collected in data summary reports.

Cognitive interviews: After each interview, the interviewer will complete a debriefing form to identify 1) SLAQ modifications, and 2) Type 1 or 2 symptom assignment. The debriefing forms from each interview will be summarized after each set of 10 interviews to determine the main themes, problems with the patient-reported outcomes measures that arose during the interviews, and suggested modifications to the measures. Following the second round of interviews, it will be determined if an additional 6 interviews are needed to assess the revised measure.

Aim 2: Develop a preliminary parsimonious measure to rapidly assess Type 1 and 2 SLE activity.

We will analyze data collected through the Duke Lupus Registry (DLR) (IRB Pro00008875) and Sub-studies of the DLR (IRB Pro00094645). Working closely with the Duke Center for Health Measurement, [name] will use patient- and physician-reported data collected from 800 patient visits in DLR to develop an effective and efficient indicator of Type 1 and Type 2 SLE activity.

Data Collection: Age, gender, race/ethnicity, employment status, marital status, living arrangement, and medication adherence will be ascertained by self-report. In addition, the DLR collects information from medical records including: insurance, medication details, disease duration, and comorbidities. The DLR also collects the following information at each clinic visit:

- **Patient-Reported Measures:** Modified Systemic Lupus Activity Questionnaire (SLAQ), Fibromyalgia Severity Scale, Patient global assessment, current medications

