- **Physician-reported measures:** Systemic Lupus Erythematosus Disease Activity Index (SLEDAI), Physician's Global Assessment, LFA-REAL
- **Routine Lupus Labs:** CBC with differential, creatinine, C3 and C4, anti-dsDNA antibody, C-reactive protein, sedimentation rate, complete urinalysis, and urine protein:creatinine

Data Analysis: Robust cluster analysis. [name] will expand on our preliminary cluster analysis using latent profile analysis to include detailed patient-, physician- and laboratory measures. **Power Calculation:** In order to identify 4 clusters using 8 predictive variables, a minimum sample size of 320 patients is needed. If the cluster analysis identifies 7 distinct clusters, there will be sufficient power to include 5 predictive variables in the model with 350 patients. Differences in phenotypes across clusters, including patients' demographic, SLE history, patient- and physician-reported measures, and laboratory tests will be estimated by ANOVA and Chi-squared test.

Using our new knowledge about the quantitative differences in SLAQ responses by cluster, the qualitative information about symptoms from patient interviews, and clinical expertise, we will revise the SLAQ and create a new scoring system with individual Type 1 and 2 SLE scores. This new scoring system will be tested using 800 patient visits to determine if the new Type 1 and 2 SLE scores correspond to cluster assignment. Using logistic regression models, [name] will compare three commonly used physician-reported SLE measures, the SELENA-SLEDAI, physician's global assessment, and LFA-REAL™ to determine if model fit improves with physician-reported measures. Goodness of fit will be assessed by the Hosmer-Lemeshow chi-square test, and model discrimination will be assessed using C statistics to estimate the area under the receiver operating characteristic curve. To account for patients potentially contributing more than one visit to this analysis, generalized estimating equations (GEE) will be used.

Inclusion: Patients who are enrolled in the Duke Lupus Registry and gave informed consent through the Duke Lupus Registry (DLR) (IRB Pro00008875) and Sub-studies of the DLR (IRB Pro00094645).

Compensation: Data collected from patients enrolled in the Duke Lupus Registry will be retrospectively analyzed. No compensation will be provided as part of this analysis.

Aim 3. Conduct a pilot implementation study of the Type 1 and 2 SLE model into clinical care.

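### Does Aim 2's sample-size statement need redoing because it claims power without inputs and counts patients while the analysis uses visits?

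*Combined protocol and SAP*

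**What the plan says.** All of this is in Methods, Aim 2, unless noted.

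- Under the power-calculation label in Data Analysis: "In order to identify 4 clusters using 8 predictive variables, a minimum sample size of 320 patients is needed". Then: "If the cluster analysis identifies 7 distinct clusters", "there will be sufficient power to include 5 predictive variables in the model with 350 patients".
- The clustering method is latent profile analysis (LPA) on patient, physician and laboratory measures.
- The opening paragraph bases the work on "data collected from 800 patient visits in DLR". Data Collection says that the registry records the patient-reported measures, physician-reported measures and routine laboratory tests at each clinic visit.
- The revised scoring is to be "tested using 800 patient visits to determine if the new Type 1 and 2 SLE scores correspond to cluster assignment". Logistic models with C statistics follow. "To account for patients potentially contributing more than one visit to this analysis", generalized estimating equations (GEE) are used.
- Background & Significance states: "We hypothesize that Type 1 and 2 SLE activity varies in intensity over time".
- The aim itself is modest: "Develop a preliminary parsimonious measure to rapidly assess Type 1 and 2 SLE activity". The Compensation paragraph says that the registry data are analysed retrospectively.

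**The concern.** Two things catch the eye.

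First, a claim of sufficient power normally rests on a target power, an effect size and a decision rule. For LPA these would be the separation and relative sizes of the classes and the criterion that picks their number. None is given, so a reader could take the sentence for a calculated assurance that the document does not contain.

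Second, the units differ. The sample size is in patients, while the score test compares scores with cluster assignment across 800 visits, so each visit needs a cluster. If the LPA used one visit per patient, no written step assigns the remaining visits, and carrying a patient's cluster to later visits would sit badly with the hypothesis that activity varies over time. If the LPA used all visits, 320 or 350 is not the number of records clustered, and correlated visits enter a model for which GEE is not mentioned. If cluster assignment is the outcome of the logistic models, which is a fair inference although the plan does not name the outcome, the C statistics could depend on the choice.

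**Working it through.** **1. Reproducing the plan's figures.** The inputs are 4 clusters, 8 variables, 320 patients; and 7 clusters, 5 variables, 350 patients. Try N = 10 × clusters × variables:

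- 10 × 4 × 8 = 320
- 10 × 7 × 5 = 350

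Both match exactly. Other simple rules do not give both, with k clusters and p variables:

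| Rule | First scenario | Second scenario |
|---|---|---|
| Plan | 320 | 350 |
| 10kp | 320 | 350 |
| 2^p | 256 | 32 |
| 5 × 2^p | 1280 | 160 |
| 70p | 560 | 350 |
| 20kp | 640 | 700 |
| 10k(p+1) | 360 | 420 |

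Read this way, the second sentence limits the number of variables: 350 / (10 × 7) = 5. The rule is inferred from the arithmetic, and an unreported calculation cannot be excluded. With equal clusters the figures mean 320/4 = 80 and 350/7 = 50 patients per cluster.

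**2. Can the power claim be tested?** Not from the documents. The simulation here rests on assumed conditions: equal class probabilities, independent unit-variance normal variables, random class centres scaled to a given mean pairwise distance, and BIC choosing among 1 to k+1 classes. The share of runs selecting the true number was:

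| Mean separation (SD) | 4 clusters, 8 variables, N = 320 (30 runs) | 7 clusters, 5 variables, N = 350 (20 runs) |
|---|---|---|
| 2 | 0% | 0% |
| 3 | 40% | 0% |
| 4 | 90% | 5% |
| 5 | not run | 40% |

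Monte Carlo error at 40% is √(0.4 × 0.6/30) = 9 points and √(0.4 × 0.6/20) = 11 points. The answer depends on the assumed geometry, which the plan does not give. The table therefore neither supports nor refutes either figure.

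**3. One visit per patient in the LPA.** With n distinct patients, 800 − n visits lie outside the fit. That would be 480 (60%) at n = 320, 450 (56%) at n = 350 and 0 at n = 800. The plan does not state n; 320 is a minimum and 350 a what-if, so none of these is an estimate. Nor are these visits unclassifiable. A fitted LPA gives posterior class probabilities for any record with the same variables, and Data Collection provides those variables at each visit. Each visit is then classified on its own data, which also respects activity that varies over time.

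**4. All visits in the LPA.** Every visit then gets a cluster directly. As a rough guide to information, take m = 800/n visits per patient, within-patient correlation ρ (not in the plan) and effective N = 800 / (1 + (m − 1)ρ):

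| ρ | n = 320, m = 2.5 | n = 350, m = 2.29 |
|---|---|---|
| 0.3 | 552 | 577 |
| 0.5 | 457 | 487 |
| 0.7 | 390 | 421 |
| 0.9 | 340 | 371 |

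At ρ = 1 the formula returns 800/m = n. On this guide, using all visits carries no less information than the patient count, so a figure in patients is a cautious floor.

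**The case for a change.** The strongest case for a change is that the wording promises something the document cannot back and that the repair is cheap: a different label, a count of patients already in the registry, and a sentence on the unit. Two analysts following this text could cluster differently and report different C statistics. The GEE sentence does not settle it, since GEE handles correlation in a regression and neither sets the clustering unit nor assigns visits. With all visits pooled, an information criterion that treats records as independent may also be affected when the number of classes is chosen.

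Much of this is true as description. The power wording is unsupported, the unit is unstated, and GEE is written only for the later regression. It does not amount to an error in a stated method. No rule in the plan is shown to give a wrong result, and both readings of the unit lead to a workable analysis with standard tools. Using 800 visits to develop the indicator makes the all-visits reading a natural one. A repeat LPA on one visit per patient, or a bootstrap of cluster stability, would be reasonable sensitivity work, but it would be an addition resting on a choice the plan has not made.

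**Conclusion.** No change to the plan follows. The power label is loose: 320 and 350 fit a ratio of ten patients per variable per cluster, and no power input is given. Neither figure is shown to be miscalculated or too small, and rewording would alter no recruitment, test or estimate in a retrospective analysis for a preliminary measure. The unit of the LPA is a gap that an analyst can fill sensibly, because the clustering measures are recorded at every visit. The size of any effect on the C statistics cannot be given: it depends on the number of distinct patients, the visits per patient and the within-patient correlation, none of which is stated. The conclusion assumes that the measures are complete enough at each visit to be classified, as Data Collection implies. The number of patients, the clustering unit and the way visits were assigned belong in the report of the results.

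### Aim 2 tests cluster differences on the same kinds of measure that form the clusters; for any clustering indicator the p-value is circular and is not evidence of distinct phenotypes

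*Combined protocol and SAP*

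**What the plan says.** Under Aim 2, Data Analysis, the preliminary cluster analysis is to be extended "using latent profile analysis to include detailed patient-, physician- and laboratory measures". The Power Calculation gives two scenarios. The first reads "In order to identify 4 clusters using 8 predictive variables, a minimum sample size of 320 patients is needed"; the second is 7 clusters, 5 variables and 350 patients. The next sentence compares the clusters on demographics, SLE history and the three classes of measure already named for the LPA: "patient- and physician-reported measures, and laboratory tests will be estimated by ANOVA and Chi-squared test".

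The plan does not list the indicators, keep any measure back as external, or call these comparisons descriptive. The cluster differences are then used. The paragraph on revising the SLAQ opens "Using our new knowledge about the quantitative differences in SLAQ responses by cluster" and adds the patient interviews and clinical expertise as further inputs.

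Under Background & Significance the underlying model is dimensional: "we have developed a new conceptual model that characterizes SLE activity into two dimensions". It continues: "We hypothesize that Type 1 and 2 SLE activity varies in intensity over time".

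**The concern.** ANOVA and chi-squared assume that group membership was fixed without reference to the variable being compared. LPA chooses the groups so that its indicators differ between them. A small p-value on an indicator therefore follows largely from how the groups were made, whether or not discrete phenotypes exist.

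The problem is confined to indicators. Demographics, SLE history and any measure left out of the LPA are not tested circularly. A left-out measure that is correlated with the indicators will still differ across arbitrary cuts of a continuum.

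The model is stated as two dimensions varying in intensity, so a continuum without discrete clusters is a live alternative. These tests cannot exclude it. The risk is that small p-values are read as confirming distinct Type 1 and Type 2 phenotypes, and that this reading carries into the SLAQ revision and the new scores.

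**Working it through.** **Inputs.** The two scenarios (4 clusters, 8 variables, 320 patients; 7 clusters, 5 variables, 350 patients) come from the Power Calculation. Normal indicators, the correlations, the cluster separations and the 0.05 level are assumptions; the documents give none of them.

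**1. The plan's own figures.** 10 × clusters × variables gives 10 × 4 × 8 = 320 and 10 × 7 × 5 = 350. Both reproduce. The rule is inferred, since no formula is stated. Here the figures only set the size of the simulations.

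**2. The test.** For N patients in K clusters, F = [Σ n_k(x̄_k − x̄)²/(K−1)] ÷ [ΣΣ(x_ik − x̄_k)²/(N−K)]. It is referred to F with 3 and 316 degrees of freedom in the first scenario, and 6 and 343 in the second. That reference holds only if the labels do not depend on x. For an LPA indicator they do.

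**3. No true clusters, number of classes fixed at the plan's scenarios.** LPA was fitted by EM with local independence and class-equal variances, followed by modal assignment and one-way ANOVA.

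| Patients / variables / classes | Correlation | Datasets | Indicators p<0.05 | Indicators p<0.001 | Unrelated outside variable p<0.05 |
|---|---|---|---|---|---|
| 320 / 8 / 4 | 0 | 200 | 87.4% | 72.6% | 6.5% |
| 320 / 8 / 4 | 0.3 | 200 | 100% | 100% | 3.0% |
| 350 / 5 / 7 | 0 | 60 | 98.0% | 93.3% | 3.3% |
| 350 / 5 / 7 | 0.3 | 40 | 100% | not recorded | 5.0% |

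The simulation error on a true 5% rate is √(0.05 × 0.95/200) = 1.5 percentage points with 200 datasets and √(0.05 × 0.95/40) = 3.4 with 40, so the last column is compatible with 5%. A repeat with separate code, 200 datasets per setting, gave 89.9%, 100%, 99.8% and 100% for indicators, and 4.3% to 5.4% for unrelated variables. At correlation 0.3, left-out variables sharing the common factor were significant in 100% of tests.

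**4. No true clusters, number of classes chosen by BIC** (1 to 7 classes, 320 patients, 8 variables).

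- Independent indicators: one class in 40 of 40, so no comparison arises.
- One continuous factor, correlation 0.3: 2, 3 or 4 classes in 1, 38 and 1 of 40; 100% of indicators at p<0.05.
- Two uncorrelated continuous factors, four indicators each, by within-factor correlation:
  - 0.16: more than one class in 36 of 40; 75% of indicators at p<0.05.
  - 0.30: 2, 3 or 4 classes in 1, 45 and 14 of 60, so 3 or 4 in 45 + 14 = 59; 99.4% of indicators.
  - 0.49: 4 to 7 classes in 60 of 60; 100% of indicators.

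Repeats of the 0.30 case gave 3 or 4 classes in 30 of 30, 40 of 40 and 20 of 20 datasets.

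**5. Four real clusters** (Type 1 low/high by Type 2 low/high), 320 patients, 7 true indicators and 1 pure-noise indicator, 4 classes, 200 datasets per setting. The noise indicator reached p<0.05 in 72.5%, 25.0%, 7.5% and 4.5% at separations of 1, 1.5, 2 and 3 SD. An unrelated outside variable did so in 4% to 8%. A repeat with 100 datasets per setting gave 67%, 31%, 14% and 5%. A further run of the first two separations gave 55% and 27%. The pattern is stable, but the individual percentages are approximate.

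**The case against.** The strongest reply is that the plan speaks of estimating differences, sets no significance level or decision rule for them, and never says that a p-value proves the clusters distinct. A descriptive profile table is a fair reading. That stands as a reading, but the methods named are hypothesis tests and carry no caveat. If description is intended, saying so costs a sentence.

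Second, the overlap is by class of measure and its extent is unknown. The plan lists more measures than 8. The SLAQ has 24 symptoms, so most item-level SLAQ comparisons may not be on indicators; if a SLAQ total were an indicator, its items would still be tied to it. The plan also does not say that p-values select SLAQ items. All of this stands, and it limits the reach of the concern.

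Third, the 87% and 98% need both independent indicators and a forced number of classes. The 4 and 7 are sample-size scenarios, and under independence BIC would stop at one class. This also stands. However, measures of one disease are unlikely to be independent, and the plan states no selection criterion.

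Fourth, the BIC results depend on local independence, the usual LPA default. With a shared full covariance and the same two-factor data at 0.30, BIC over 1 to 3 classes chose one class in 40 of 40. The plan specifies neither structure, so part of the problem lies in how classes are counted.

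Finally, the Background passage on intensity concerns change over time and goes on to minimal and mixed states, which fits discrete states too. A continuum is therefore an alternative to be excluded, not an established fact.

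**Conclusion.** The concern holds, limited to variables used as LPA indicators. As written, the plan produces p-values for them that have no valid null. With no clusters and the number of classes fixed, 87% to 100% of indicators test significant at a nominal 5%. With two continuous dimensions, local independence and BIC selection, 75% to 100% do so over the correlations tried (0.16 to 0.49). With real clusters, a noise indicator is badly inflated at 1 SD separation (55% to 73% across runs) and near nominal at 3 SD (about 5%). How misleading the tests would be depends on correlations, separation and a class-selection rule that the documents do not give. This should be changed before the analysis, but it does not undermine the aim.

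**What to change.** In Aim 2, Data Analysis:

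- Name the LPA indicators.
- Report the indicators by cluster descriptively, as posterior-weighted means or proportions with standardised differences and no p-values.
- Confine ANOVA and chi-squared to variables not used in the LPA (demographics, SLE history, held-out measures), preferably with a three-step or posterior-weighted method that carries classification uncertainty.
- State that no between-cluster p-value is evidence that the clusters are distinct.
- Settle the unit of analysis. The 320 and 350 are patients, but Aim 2 opens by describing "patient- and physician-reported data collected from 800 patient visits in DLR". If the comparison pools several visits per patient, use one visit each or patient-clustered standard errors. The sentence "To account for patients potentially contributing more than one visit to this analysis, generalized estimating equations (GEE) will be used" follows only the scoring models.

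The cost is analysis wording, with no extra data. Fewer p-values will be reported, and held-out measures correlated with the indicators will still differ and need cautious reading. The change does not itself settle clusters against continuum; it stops these tests from being taken as the answer.

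### Latent profiles are compared as if membership were observed: differences on variables outside the profile model shrink, differences on the profile indicators are inflated

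*Combined protocol and SAP*

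**What the plan says.** All of this is in the combined protocol and SAP, Aim 2, Data Analysis, unless another place is named.

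- The earlier cluster analysis is to be extended "using latent profile analysis to include detailed patient-, physician- and laboratory measures". No list of indicators is given.
- On size: "In order to identify 4 clusters using 8 predictive variables, a minimum sample size of 320 patients is needed". For seven clusters, "there will be sufficient power to include 5 predictive variables in the model with 350 patients".
- The variables to be compared across clusters are described as "including patients' demographic, SLE history, patient- and physician-reported measures, and laboratory tests", and the differences "will be estimated by ANOVA and Chi-squared test".
- The SLAQ is then revised and rescored. One stated input is "Using our new knowledge about the quantitative differences in SLAQ responses by cluster". The Data Collection paragraph lists a modified SLAQ among the patient-reported measures.
- The scores are tested on 800 visits "to determine if the new Type 1 and 2 SLE scores correspond to cluster assignment", with logistic models, the Hosmer-Lemeshow test and C statistics.
- The one stated adjustment is GEE, for patients who contribute more than one visit.

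The plan mentions no posterior probabilities, entropy, classification-quality check or correction for misassignment.

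**The concern.** Latent profile analysis gives each case a probability of belonging to each profile. ANOVA, chi-squared and a logistic model of cluster assignment need one label per case. The natural reading is that each case takes its most probable profile and that the label is then treated as data.

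This has two consequences, in opposite directions. Variables that played no part in forming the profiles are compared between groups contaminated by misassigned cases, so real differences look smaller. Variables that did form the profiles are compared between groups that were chosen to differ on them, so differences look larger and p-values lose their meaning. The list of variables to be compared covers both kinds and does not separate them.

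At stake is the description of who falls into which profile, and confidence in a scoring system whose agreement with the profiles is judged by a C statistic.

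**Working it through.** **The plan's own figures.** No alpha, power or effect size is stated. Both sample sizes match 10 × clusters × variables: 10 × 4 × 8 = 320 and 10 × 7 × 5 = 350. That rule is an inferred match. It says nothing about how accurately cases will be classified.

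**Assumptions.** The documents give no separation or entropy, so a range is shown. There are four equal profiles (minimal, Type 1 only, Type 2 only, mixed) and 8 normal indicators with unit SD, four per axis.

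**External variables, by formula.** Let q be the chance of being placed correctly on one axis, so accuracy is q². Let the external variable be 1.0 SD higher in the mixed profile than in the other three. Among cases labelled mixed, a share q² is truly mixed. Among cases labelled Type 2 only, the share is q(1 − q). The expected difference is q² − q(1 − q) = q(2q − 1). The simulated columns come from 400 data sets of 350 patients, with posteriors computed at the true parameters.

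| Accuracy | Entropy | q | q(2q − 1) | Hard labels, simulated | BCH, simulated |
|---|---|---|---|---|---|
| 71% | 0.49 | 0.843 | 0.58 | 0.57 | 1.00 |
| 78% | 0.61 | 0.883 | 0.68 | 0.67 | 0.98 |
| 87% | 0.76 | 0.933 | 0.81 | 0.82 | 1.02 |
| 95% | 0.91 | 0.975 | 0.93 | 0.94 | 1.01 |

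With 320 patients, the figure that the plan pairs with four clusters, hard labels give 0.57, 0.69, 0.82 and 0.94, and BCH gives 0.98 to 1.01.

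The size depends on the pattern of the external variable. If it follows one axis only, the retained difference across that axis is 2q − 1: 0.69, 0.77, 0.87 and 0.95. With symmetric error e it is 1 − 4e/3: 0.61, 0.71, 0.83 and 0.93. The direction is the same in all three.

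**External variables, model fitted.** Here the profile model was estimated by EM (320 patients, 150 data sets per setting). The external means were 0, 0.5, 0.5 and 1.0, and the contrast is mixed minus minimal, with true value 1.00.

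| Indicator separation (SD) | Misclassified | Hard labels | BCH (median) |
|---|---|---|---|
| 1 | 36% | 0.61 | 0.80 |
| 1.25 | 23% | 0.78 | 0.96 |
| 1.5 | 14% | 0.87 | 0.99 |
| 2 | 5% | 0.95 | 0.97 |

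**Opposite direction for indicators.** This is eta-squared from the same fitted model, under assigned and under true profiles.

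| Separation (SD) | External: assigned / true | Ratio | Indicators: assigned / true | Ratio |
|---|---|---|---|---|
| 1 | 0.051 / 0.122 | 0.42 | 0.276 / 0.206 | 1.34 |
| 1.5 | 0.090 / 0.117 | 0.77 | 0.395 / 0.365 | 1.08 |
| 2 | 0.112 / 0.123 | 0.91 | 0.512 / 0.503 | 1.02 |

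With no true profiles at all, ANOVA at 0.05 rejected for 86% of indicators and 3% of external variables.

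**C statistic.** A simple sum of the four Type 2 indicators, used to predict membership of a high Type 2 profile, gave 0.961 against assigned and 0.923 against true profiles at 1 SD, and 0.998 against 0.983 at 1.5 SD. The sum was not tuned to the data, so the excess comes from score and label sharing the same measurements. For an external predictor of the mixed profile the bias was downward: 0.612 against 0.675 at 1 SD.

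**Posterior weights without correction.** On the mixed-versus-Type-2 contrast, weighting by posterior probability gave 0.43 against 0.58 from hard labels at 71% accuracy, 0.58 against 0.69 at 80%, and 0.82 against 0.88 at 92%.

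**Precision.** At 71% accuracy the SD of the BCH estimate was 0.29 against 0.16 for hard labels (0.29 / 0.16 = 1.81). At 95% it was about 6% wider. Root mean squared error favoured BCH at accuracies of about 71% to 87% and was equal at about 95%.

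**The case against.** The strongest reply has four parts.

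- *The size is unknown.* This stands. The loss runs from 43% to 6% of the difference across the assumed range, and at entropy of about 0.9 or above it is small.
- *Only descriptive comparisons are affected.* This largely stands for the external variables. Demographics and SLE history describe the profiles of a preliminary measure, and no decision rule rests on them. It limits the weight of the point but does not make the planned estimates unbiased.
- *Hard assignment is not stated.* True. It is inferred from the plan's phrase "new Type 1 and 2 SLE scores correspond to cluster assignment" and from the choice of tests. If another method is intended, the plan should say so.
- *The correction is imperfect.* True. The values near 1.00 use true parameters. With an estimated model at the poorest separation BCH reached 0.80, which is still better than 0.61 without it.

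A reader might go further and infer that every planned comparison, the logistic models included, understates the true differences, and that the shrinkage carries into the new scores. The documents do not support that. The profile model draws on patient-, physician- and laboratory measures, and the SLAQ is a patient-reported measure. If SLAQ items are indicators, the likely error in the scoring step is optimism. A reader might also take mixed versus Type 2 only to be the study's key contrast. The Background section hypothesises mixed activity, but it states the objective as separating Type 1 from Type 2. That contrast is used above only as an illustration.

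**Conclusion.** The point holds in a limited, two-directional form. The plan treats estimated profiles as observed groups. For variables outside the profile model this biases differences towards zero; for the model's own indicators, and for the C statistic of scores built from them, it biases upward. The external loss is about 0.43 SD of a true 1.0 SD difference at 71% accuracy and 0.06 SD at 95%.

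These sizes rest on assumed separations, four equal profiles, 8 normal indicators, and assignment to the most likely profile. How far the upward bias reaches the new scores depends on whether SLAQ items are indicators, which the plan leaves open. The change is advisable and cheap. It is not a reason to doubt that Aim 2 can be done.

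**What to change.** In Aim 2, Data Analysis:

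1. State which variables are profile indicators and which are external, and how cases are assigned to profiles.
2. For external variables, replace ANOVA and chi-squared on assigned clusters with a BCH or maximum-likelihood three-step comparison.
3. Report indicator differences across profiles as description, without p-values. Present the C statistic of any score built from indicators as optimistic; the three-step method does not correct it.
4. Report entropy and average posterior probabilities. Read entropy with care: at 1 SD separation the fitted model showed 0.59, against 0.49 at the true parameters.
5. Do not use uncorrected posterior-probability weights in place of the three-step method.

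No new data are needed, and the method is a standard option in latent-class software. The price is precision: standard errors about 80% wider at 71% accuracy and about 6% wider at 95%. Recovery is incomplete when separation is poorest (0.80 of a true 1.00, against 0.61 uncorrected). If entropy proves to be about 0.9 or higher, the results will change little.
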